1.3 Planned analyses

Unblinded analyses corresponding to the primary and secondary objectives will be performed by the investigative team only after data are available from all participants and the SAP is finalized.

2. GENERAL CONSIDERATIONS FOR DATA ANALYSES

2.1 Estimands of interest

All primary analyses will be intention-to-treat (ITT) in nature, maintaining fidelity to randomized group. Per-protocol analyses may be performed as a sensitivity analysis.

2.2 Analysis sets

We characterize different study subsets for purposes of analysis in Table 2.

2.3 Missing data

- Subject visits might not occur on protocol-specified days. We will characterize the extent to which visit dates were faithful to the pre-specified protocol windows; for the purpose of analysis, observations will be mapped to their “nearest” protocol-defined study visit window within a tolerance of at most ten days for Visits 1, 2, and 3. The study day as defined in Section 1.1.2 will be used when data are summarized by visit.
- A missing pre-treatment laboratory result would be treated as normal (i.e., no toxicity grade) for the laboratory abnormality summary.
- To account for other missing data (e.g., in immunogenicity data), we will employ multiple imputation with chained equations using at least fifty imputation iterations, aggregating via Rubin’s rules; we will also compare these results to those of a complete-case analysis (the latter of which being a secondary approach for the purposes of a sensitivity analysis).

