## 2. Prior Influenza Vaccine Trials in HSCT Recipients:

Influenza vaccination is the primary mode for prevention of influenza infection. Protection is primarily mediated by virus-specific antibodies that depend on an intact humoral response. Both B cell and T cells responses are impaired in HSCT recipients, functional recovery of B and T lymphocytes can take up to 2 years or even longer. Limited data are available regarding influenza vaccine responses in pediatric HSCT recipients because the majority of influenza vaccine trials have been conducted in adult HSCT recipients. Only 5 of these trials included children, and only one exclusively included children, with total enrollment of 5 subjects. Therefore, dedicated influenza vaccine trials in pediatric HSCT patients are needed.

Despite limited clinical data for influenza vaccine efficacy in this population, yearly vaccination is recommended, beginning 3-6 months after HSCT. However, the optimal post-transplantation vaccine schedule has not been established. Existing data for influenza vaccination in HSCT recipients are primarily from subjects who received influenza vaccination between 6 months and 3 years after HSCT. Thus, little data exist to support vaccinating pediatric HSCT recipients earlier than 6 months or later than 3 years post-transplant. The percentage of HSCT recipients that achieve seroprotective hemagglutinin inhibition (HAI) titers (defined as  $\geq 1:40$ ) one month after standard influenza vaccination is very low when compared to healthy controls. While this impaired vaccine-induced immune response is likely due to incomplete immune reconstitution or immunosuppressive therapies, the exact immune mechanisms of HSCT recipients' poor response to influenza vaccination are not well described. Notably, graft versus host disease (GVHD), low number of CD19+ B cells, and earlier timing of vaccination post-transplant have been implicated as factors associated with lower titers after influenza vaccine.

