## Proven clinical influenza illness is any breakthrough influenza illness confirmed by laboratory testing (i.e. Rapid antigen assay, PCR, virus culture, ,etc.

^^ Optional for repeaters in the 2019-20 season

**5. Treatment Groups:** There will be two groups – HD-TIV versus standard dose QIV. The children will be randomized in a 1:1 HD-TIV (100 subjects) versus standard dose QIV (100 subjects) for current enrollment season.

Treatment Group	Target # (all study years)
Group 1 0.5 mL HD-TIV	100
Group 2 0.5 mL standard dose QIV	100

**a. Randomization:** Subjects will be randomized 1:1 to either HD-TIV or standard dose QIV. Randomization will be frequency-matched within each site to ensure balance between the groups and will be implemented using the Randomization Module within Vanderbilt's REDCap database. The investigational pharmacy at each of the 9 institutions will distribute the assigned study vaccine. Because we are evaluating the immunogenicity of early timing of influenza vaccine post-transplant, we will limit enrollment to 60 (30%) subjects to  $\geq 12$  months post-transplant.

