**8. Study Withdrawal / Discontinuation:**

**a. Reasons for Withdrawal or Discontinuation of Study Product**

- 1. Subjects will be able to withdraw from the study at any time point.
- 2. A study subject will be discontinued from participation in the study if the following occur:

- a. Any clinical adverse event (AE), laboratory abnormality, intercurrent illness, or other medical condition or situation occurs such that continued participation in the study would not be in the best interest of the subject. However, the subject may continue to be followed for safety purposes.
- b. Development of any exclusion criteria may be cause for discontinuation from the study, except for individuals who were 17 at enrollment and turned 18 year old during the study.
- c. Subjects may be removed from the study for failure to make follow-up visits.
- d. Subjects may be removed from the study if new information becomes available that makes further participation unsafe.

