## **17. Statistical Considerations:**

- a. **Sample Size Calculations:** A total of 200 children will be targeted, with 100 in each group. This is based on the assumption, with 80% power, that 20% of the children in the standard dose group will achieve a protective titer compared to 40% of the HD-TIV group for at least one influenza antigen. Accounting for a 20% drop out rate, 100 children in each group will be needed.

Strain	Expected Seroprotection HD-TIV	Expected Seroprotection standard dose	N (HD)	N (SD)	Power	Total N with 20% drop out
Expected HD-TIV seroprotection is twice as of standard dose						
A	40%	20%	80	80	80%	200
A	50%	25%	55	55	80%	138
A	60%	30%	40	40	80%	100
A	70%	35%	28	28	80%	70

- b. **Immunogenicity analysis:** The probability of achieving a 4-fold (or greater) rise in post-vaccination HAI titers relative to baseline, as well as the probability of a HAI titer greater than

1:40, will be estimated using a binomial model. We will calculate the Bayesian posterior distribution of the probabilities under all 4 combinations of standard and HD-TIV crossed with a single dose and two doses. From these probabilities, odds ratios will be calculated along with 95% credible intervals. These quantities will be modeled as a logit-linear function of several covariates, including CD4+/CD8+/CD19+ and IgG levels, absolute neutrophil and lymphocyte count (or their ratio), time from post-transplant to enrollment, type of preparative regimen, donor status, and stem cell source. In addition, the distributions of geometric mean HAI titers for high and standard dose recipients will be estimated via log-normal models and expressed as ratios in order to evaluate the evidence for higher GMT in the HD-TIV sample, after one and two vaccines. In addition, we will compare each group to document if they meet serological criteria by WHO biological standards for influenza vaccines (>40% for seroconversion, GMT >2.5-fold increase, and >70% with  $\geq 1:40$ ).

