2.5 Hypothesis testing

All tests will be conducted with a nominal significance level of $\alpha = 0.05$ (two-sided).

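### The only planned check on missing titers, imputation against complete case, cannot test whether informative Visit 3 dropout has biased the primary ratio

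*SAP*

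**What the plan says.** SAP 2.3 handles missing immunogenicity data by multiple imputation with chained equations, at least fifty imputations, combined by Rubin's rules. It then adds "we will also compare these results to those of a complete-case analysis" and gives that comparison the role of sensitivity analysis. It does not list the variables in the imputation model, state a missingness assumption, or say whether complete case means complete children or available visits.

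The SAP's other sensitivity analyses address different questions: adherence (2.1, optional), outliers (2.6, optional) and values at the upper limit of detection (2.7). None concerns missing titers.

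On how titers may go missing, Protocol 17.a says "Accounting for a 20% drop out rate, 100 children in each group will be needed". Protocol 8.a discontinues a child if "Any clinical adverse event (AE), laboratory abnormality, intercurrent illness, or other medical condition or situation occurs such that continued participation in the study" would not serve that child's interest. Protocol B.2 names GVHD, low CD19+ B-cell numbers and "earlier timing of vaccination post-transplant have been implicated as factors associated with lower titers after influenza vaccine".

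On mitigation, Protocol 8.b and 13.e ask sites to keep trying to obtain post-vaccination blood after withdrawal. Protocol C.1 and Table 3 schedule CD4, CD8, CD19, IgG and IgM at every main visit. Protocol 14 has GVHD changes documented at Visit 2.

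**The concern.** A sensitivity analysis for missing data should ask what happens if the main analysis's untestable assumption is wrong. Here that assumption is that, given what the imputation model contains, a child with no Visit 3 titer would have had a titer like those observed. Complete case does not drop the assumption. It usually strengthens it, because it conditions on less.

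The protocol's own account makes informative dropout possible: children may leave because they are ill, and conditions of impaired immunity go with lower titers. If the missing children have lower titers than their recorded data predict, and the rate or depth differs by arm, the H1N1 and H3N2 ratios behind the primary objective are biased. The planned comparison might show little difference, and a reader might take that as evidence of robustness.

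**Working it through.** All figures concern the Visit 3 HD-TIV to SD-QIV geometric mean ratio, the comparison that SAP 1.2.1 makes primary. How SAP Table 3 maps it to model parameters is a separate matter.

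**Step 1. The plan's own figure.** Protocol 17.a assumes that "20% of the children in the standard dose group will achieve a protective titer compared to 40% of the HD-TIV group", with 80% power. SAP 2.5 gives two-sided 0.05. With unpooled variance:

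n = (1.960 + 0.842)² × (0.4×0.6 + 0.2×0.8) / (0.4 − 0.2)² = 7.849 × 0.40 / 0.04 = 78.5, so 79 per arm against the stated 80.

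Inflating for dropout, 80 / (1 − 0.20) = 100 per arm, 200 in total. The plan's figure reproduces. The 20% is one overall allowance, with no split by arm or reason.

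**Step 2. The two assumptions side by side.**

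- Imputation: Visit 3 missingness is unrelated to the missing titer, given everything in the imputation model.
- Complete case: the same, given only arm and the analysis covariates.

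Neither allows missingness to depend on the unseen titer after conditioning.

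**Step 3. How the two behave.** Simulation with 100 per arm, true ratio 2.00, 50 imputations and 300 replicates per scenario. The documents give no SD, correlation or dropout strength, so these are assumed: natural-log SD 1.0, 1.5 or 2.0; Visit 2 to Visit 3 correlation about 0.66; 20% missing at Visit 3; dropout log-odds 1.2 per SD of its driver. In the table the driver acts in the HD-TIV arm only. Complete case is a regression on children with a Visit 3 titer. Entries are for SD 1.0 / 1.5 / 2.0.

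| HD-TIV dropout follows | Post-baseline data in imputation model | Imputation | Complete case | Complete case ÷ imputation |
|---|---|---|---|---|
| Unrecorded illness, before Visit 2 | none | 2.24 / 2.34 / 2.49 | 2.24 / 2.35 / 2.49 | about 1.00 |
| The missing titer, before Visit 2 | none | 2.38 / 2.54 / 2.77 | 2.38 / 2.54 / 2.77 | 1.00 |
| The missing Visit 3 titer | Visit 2 titer | 2.22 / 2.34 / 2.54 | 2.34 / 2.54 / 2.79 | 1.05 to 1.10 |
| Illness | Visit 2 titer and illness marker | 2.00 / 1.97 / 1.98 | 2.21 / 2.29 / 2.39 | 1.10 to 1.21 |
| The observed Visit 2 titer | Visit 2 titer | 2.00 / 1.95 / 1.98 | 2.22 / 2.26 / 2.43 | 1.11 to 1.23 |

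In the second row both are 19% to 39% too high (2.38/2.00 = 1.19; 2.77/2.00 = 1.39) and they coincide. In the last two rows imputation is about right and the gap is widest. The gap therefore does not track the bias in the main analysis: agreement does not show that imputation is sound, and disagreement does not show that it is wrong.

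With the same mechanism and the same 20% rate in both arms, both methods gave 1.94 to 2.02, which is almost no bias. With titer-driven dropout in both arms but rates of 10% against 30% (SD 1.5), imputation gave 2.36 and complete case 2.53.

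**Step 4. Size of the bias.** Let p be the share missing and d the amount, in log2, by which missing titers lie below their imputed values. Then

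log2(true ratio) = log2(imputed ratio) − p_HD·d_HD + p_SD·d_SD.

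Take 1.7 as the imputed ratio (the H1N1 value from the phase III trial in older adults, Protocol B.3.c) and p_HD = 0.20, with a shift in HD-TIV only:

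- d = 1: 1.7 × 2^(−0.2) = 1.7 × 0.871 = 1.48.
- d = 2: 1.7 × 2^(−0.4) = 1.7 × 0.758 = 1.29.
- Equal p and equal d in both arms: the terms cancel and the ratio stays at 1.7.

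**Step 5. The assay floor.** Sera start at 1:10 (Protocol 15.b) and SAP 2.7 sets values below the limit to half of it, which implies a floor near 1:5. Assume normal log2 titers with SD 1.9 and the planning seroprotection rates. The HD-TIV mean is log2(40) − 1.9×0.253 = 4.84. After a 2-log2 drop it is 2.84, and Φ((2.32 − 2.84)/1.9) = 39% of those titers fall below 1:5. The same sum for SD-QIV (mean 3.72, then 1.72) gives 62%. Flooring the HD-TIV values shrinks the average drop from 2 to about 1.5 log2, and 1.7 × 2^(−0.2×1.5) = 1.38. Depending on how the floor is applied, the 1.29 becomes about 1.37 to 1.39.

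**The case against.** The strongest reply is that the comparison is not empty. A reader might infer that the two analyses share one assumption and so must agree whenever illness drives dropout. The documents do not support that. The assumptions differ, and the SAP leaves the imputation variables open. If these include the Visit 2 titer or illness markers, the two analyses separate clearly, as the last two rows of the table show. Complete case is a legitimate secondary comparison and need not be removed.

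A reader might also infer that illness-driven dropout will bias this trial's ratio. That does not follow either. Bias needs a difference between arms, and the documents give a single 20% planning allowance, which is not a forecast of missing Visit 3 titers. Staff and families are blinded (Protocol 16.m), and randomization is stratified on risk factors that include steroid treatment for GVHD. Earlier trials of the two doses point in different directions: more local symptoms on high dose in adult HSCT recipients, more fatigue and body ache on high dose in pediatric organ recipients, but more fatigue and headache on standard dose in children with leukemia (Protocol B.4). In addition, discontinuation under Protocol 8.a is conditional on the child's interest, blood is sought after withdrawal, GVHD changes alone do not bar the second dose, and CD19 is measured.

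All of this stands, and it lowers the likely size of the problem. It does not give the plan a way to examine the problem. The SAP does not commit the recorded markers to the imputation model, and even a rich model leaves dependence on the unseen titer untested.

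**Conclusion.** The concern holds in limited form. As planned, the check on missing titers cannot show whether informative Visit 3 dropout has moved the primary ratio, because neither analysis departs from ignorable missingness. Whether such dropout occurs, and differs by arm, is unknown from the documents.

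The sizes in Steps 4 and 5 are illustrations. They rest on 20% of HD-TIV titers missing, a shift confined to that arm, a starting ratio of 1.7 and, for the floor, a log2 SD of 1.9. The simulated ratios rest on an assumed SD, correlation and dropout strength. That the comparison cannot test ignorability follows from the two assumptions themselves and needs none of those figures. The point touches the primary result and is cheap to address, so the plan should be changed.

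**What to change.** In SAP 2.3:

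1. Keep multiple imputation as the main method and complete case as a secondary comparison.
2. Name the imputation variables, including the Visit 2 titer and the collected CD19, IgG and GVHD data.
3. Add a delta-adjusted (tipping-point) analysis of the Visit 3 H1N1 and H3N2 titers. Lower imputed log2 titers by 0, 0.5, 1, 1.5 and 2 in HD-TIV only, in SD-QIV only and in both. Set any value below the detection limit to half that limit, as in SAP 2.7.
4. Report the smallest HD-TIV-only shift at which the 95% CI of the primary ratio includes 1.

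The cost is a few lines of text and a rerun on the imputed data sets, with no new data collected. SAP 1.3 ties unblinded analysis to a final SAP, so the change should be made before then. The downside is a little more analysis work and a result that may look less robust than the present comparison would suggest.

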2.4 Robust methods

Where applicable, we will employ robust standard errors to allow model misspecification. Similarly, use of the *t*-test will allow for unequal variances between groups. Wald-based

confidence intervals and p -values will be formed on the basis of robust variance estimates.

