**b. Secondary Objectives:**

- To determine whether HD-TIV compared with standard dose QIV will increase the probability of achieving a  $\geq 4$ -fold rise in HAI titers,  $\geq 1:40$  HAI titer, or higher GMT titers to influenza B antigens in pediatric HSCT recipients.
- To determine the frequency and severity of solicited local injection site adverse events (e.g. pain/ tenderness, redness, and swelling/Induration at injection site) with HD-TIV compared to standard QIV in pediatric HSCT recipients.
- To determine the frequency and severity of solicited systemic adverse events (e.g. fevers, headache, fatigue/malaise, nausea, body ache/myalgia, general activity level, and vomiting) with HD-TIV compared to standard dose QIV in pediatric HSCT recipients.
- To define the relationship between HAI titers, ex-vivo T and B cell phenotype, and ex-vivo influenza-specific T and B cell response in pediatric HSCT recipients receiving either HD-TIV or standard dose QIV.
- To correlate HAI responses to MN responses.
- To compare the persistence of HAI and MN titers for all four antigen seven months after the last vaccine dose.
- To compare influenza detection by PCR during influenza season in pediatric HSCT recipients receiving either HD-TIV or standard dose QIV.
- To assess HAI and MN response in children undergoing two consecutive years of vaccination using the same antigen dose.
- To evaluate neuraminidase inhibition titers (NAI) responses in children undergoing two consecutive years of vaccination and correlate them to HAI responses.

**3. Study Area:** The study will be conducted in the Outpatient Pediatric Oncology/HSCT Clinics or Clinical Trial Centers at the following sites: Table 2 includes yearly average number of HSCT transplants per site (**Table 2**).**Table 2. Sites and Average Number of Yearly Allogeneic Transplants**

Site	Average Number of Yearly transplants	Potential During Study Period
Children's Mercy Hospital	25	56
Columbus Nationwide Children's Hospital	25	56
Vanderbilt University	30	68
Children's Hospital of Philadelphia (CHOP)	35	79
Seattle Children's Hospital	50	113
St. Jude Children's Research Hospital	50	113

**Comparison of High vs. Standard Dose Flu Vaccine in Pediatric Stem Cell Transplant Recipients****DMID Protocol Number 16-0117****Protocol Version 8.0**

Date: 9/12/2019

UCSF (University of California San Francisco)	50	113
Benioff Children's Hospital		
Cincinnati Children's Hospital	90	203

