5. STATISTICAL ANALYSES FOR IMMUNOGENICITY OUTCOMES

This section presents plans for analysis corresponding to each of the primary, secondary, and tertiary objectives listed in Section 1.2.1. We utilize the following general notation to describe models of interest:

• i : indicator of subject• t : indicator of visit ($t = 2, t = 3$)• X : randomized group (0 = SD, 1 = HD)• Y : titer outcome	
• \mathbf{L} : pre-treatment covariates• γ_i : subject-specific random effect• γ_S : study site random effect• ε_{it} : error term
---	---

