5.1 Analysis of continuous HAI titer responses

We will use mixed effect models to analyze continuous titers. All comparisons will be made on the geometric mean ratio scale. Consider the following model form:

$$\log(Y_{it}) = \beta_0 + \beta_1 \mathbf{1}(X = 1) + \beta_2 \mathbf{1}(t = 3) + \beta_3 \mathbf{1}(t = 3; X = 1) + \boldsymbol{\beta}_L \mathbf{L} + \gamma_i + \gamma_S + \varepsilon_{it},$$

under which all primary and secondary aims pertaining to continuous HAI titer outcomes can be addressed. The parameters of this model and the comparisons to which they correspond are summarized in Table 3.

Any continuous variables (e.g., time post-transplant and log-transformed baseline titer) used for adjustment will be flexibly modeled using natural cubic splines with knots at the 25th, 50th, and 75th percentiles.

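### SAP 2.4 takes Wald tests from robust variances without saying how they are clustered; clustering on the nine sites with a normal cut-off would give about 9–12% type I error instead of 5%.

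*SAP*

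**What the plan says.** SAP 2.4 (Robust methods) states that, where applicable, "we will employ robust standard errors to allow model misspecification", and that Wald "confidence intervals and p -values will be formed on the basis of robust variance estimates". SAP 5.1 states "We will use mixed effect models to analyze continuous titers". Its model for log titer at visits 2 and 3 has a subject random effect and, by the notation in SAP 5, a "study site random effect". SAP 2.5 sets the level: "All tests will be conducted with a nominal significance level of" 0.05, two-sided.

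SAP Table 1 lists nine sites, and the protocol (C.5.a, Randomization) agrees: "The investigational pharmacy at each of the 9 institutions will distribute the assigned study vaccine". Children are randomized individually, 1:1 and balanced within site. Protocol Table 2 ("Sites and Average Number of Yearly Allogeneic Transplants") shows sites of very different size.

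Three things are not stated: the level at which the robust variance is clustered, any finite-sample correction, and the reference distribution (normal, or t with a given number of degrees of freedom). SAP 2.8 allows R or Stata and names no command.

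**The concern.** Children at one site share the same site effect, so under the 5.1 model they are not independent. The likelihood factors by site and no lower. An analyst who applies 2.4 literally to 5.1 can therefore arrive at a sandwich variance that sums nine site contributions. A sandwich on nine clusters is biased downward and highly variable, and a Wald test with a cut-off of 1.96 makes no allowance for either.

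The choice governs the test of the primary geometric mean ratio and the other SAP Table 3 contrasts. SAP 1.3 allows unblinded analysis once the SAP is final. A variance choice left open in the SAP would then be made with results by arm in view.

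**Working it through.** **Inputs from the documents.** Two-sided 0.05 (SAP 2.5). Nine sites, G = 9. Site weights 25, 25, 30, 35, 50, 50, 50, 90, 100, total 455 (protocol Table 2). 1:1 allocation within site. Visits 2 and 3 (SAP 5).

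**Number of children.** The protocol (section 17.a) plans 80 evaluable per arm for 40% versus 20% at 80% power. The unpooled formula reproduces this: (1.960 + 0.842)² × (0.4 × 0.6 + 0.2 × 0.8) / 0.20² = 7.85 × 0.40 / 0.04 ≈ 79. With 20% dropout, 80 / 0.8 = 100 per arm. The simulations used 160 and 200 children.

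**Assumed, because the documents do not give them.** Enrolment proportional to Table 2. One set of runs used a site intraclass correlation of 0 to 0.15 and a within-subject correlation of 0.6 to 0.8. Another used natural-log SDs of 0.4 or 0.8 (site), 1.4 (subject) and 0.9 (residual).

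**Effective number of clusters.** The squared weights sum to 28,975, so 455² / 28,975 = 207,025 / 28,975 = 7.1.

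**Analytic check, equal sites.** Treatment varies within site, so the estimate is the average of nine site-specific differences. The uncorrected sandwich divides the sum of squared deviations by G² instead of G(G − 1). The Wald statistic is then a t statistic on 8 df multiplied by √(9/8).
- Uncorrected, normal cut-off: P(|t₈| > 1.96 × √(8/9)) = P(|t₈| > 1.848) = 10.2%.
- With G/(G − 1), normal cut-off: P(|t₈| > 1.96) = 8.6%.

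Unequal sites make this somewhat worse.

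**Simulation under the null.** The contrast is β1 + β3, the visit-3 difference between arms under the 5.1 coding. Table 3 labels β3 as the primary parameter, so β1 and β3 were run as well. The main runs used REML fits and 6,000 trials per setting (Monte Carlo standard error about 0.3 to 0.4 points).

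| Variance and reference | Type I error |
|---|---|
| Site-clustered, uncorrected, normal | about 11–12% (10.1–12.2% over β1, β3, β1 + β3 and all settings) |
| Site-clustered, G/(G − 1), normal | about 9–10% (7.8–10.5% over the same) |
| Site-clustered, G/(G − 1), t on 8 df | 4.9–6.4% |
| Model-based, normal | 4.0–5.8% |
| Site fixed, robust clustered on subject | 4.9–6.3% |
| Site random, robust clustered on subject, model's own scores | 4.6–6.1% |

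In one setting (160 children, Table 2 weights, intraclass correlation 0.05), the first two rows are 11.0% and 9.1%. With 180 children and 12% of visit-3 samples missing they are 11.8% and 10.3% (1,200 trials, standard error 0.9 points). With a site SD of zero the first row is still 11.1–11.7%, so the inflation comes from having nine clusters and does not depend on how much sites differ.

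**If the treatment effect varies by site** (SD 0.2 or 0.3 of the total SD, mean effect zero), the visit-3 errors are:

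| Method | SD 0.2 | SD 0.3 |
|---|---|---|
| Model-based, normal | 7.9% | 10.6% |
| Site fixed, clustered on subject | 8.8% | 11.5% |
| Site-clustered, G/(G − 1), t on 8 df | 5.7% | 5.9% |

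**The case against.** The strongest reply is that the SAP never says it will cluster on site. Section 2.4 limits robust errors to where they apply, and randomization is by child within site, so clustering on subject is a reasonable reading with error near 5%. This stands as a limit on the claim. A reader might infer that the plan as written has an 11% type I error. The documents do not support that, because the figure needs site clustering, no G/(G − 1) factor and a normal cut-off together. With the factor alone it is about 9–10%, and with the factor and t on 8 df about 5–6%.

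A reader might also infer that subject-level clustering with the random site effect kept errs the other way and is conservative. As a general statement this fails. It happens only if the sandwich uses raw residuals that still contain the site effect. The variance is then inflated by about 1 + site variance / (1.4² + 0.9²) = 1 + site variance / 2.77. At site SD 0.4 that is 1.06 and predicts 4.4% (simulated 4.2–5.0%). At site SD 0.8, an intraclass correlation of 0.64 / 3.41 = 19%, it is 1.23 and predicts 3.0% (simulated 2.8–3.8%). With the model's own scores the treatment tests are near nominal. If the effect varies by site, subject clustering becomes anti-conservative (8.4–11.5% for the visit-2 and visit-3 contrasts).

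Finally, the inflation cannot be carried over by number to the logistic models of SAP 5.2 and 5.3, or to estimates pooled by Rubin's rules under SAP 2.3, because neither was simulated.

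**Conclusion.** The point holds in conditional form. SAP 2.4 and 5.1 together leave the variance of the primary test open, and the level at which the 5.1 likelihood factors is one of the readings they permit. Under that reading with a normal cut-off, the two-sided error is about 11–12% uncorrected, or about 9–10% with G/(G − 1), against a stated 5%. The result rests on nine sites, enrolment in proportion to protocol Table 2, assumed SDs and the log-titer model only. It changes little over the SDs tried.

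This is more than a missing detail, because a literal application of the text can roughly double the error of the primary test. It should be settled in the SAP before unblinded analysis. It does not show that the analysis will be wrong.

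**What to change.** In SAP 2.4 and 5.1, state the clustering level, the small-sample correction and the reference distribution. Rule out site-clustered Wald tests with a normal reference. Then name one method:

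- **(a)** Site random, model-based REML variance, with a small-sample degrees-of-freedom correction. Cost: less of the protection against misspecification that 2.4 is meant to give.
- **(b)** Site as a fixed effect, robust variance clustered on subject; about 5–6% error under a common treatment effect. Cost: eight extra parameters.
- **(c)** Site clustering with a small-sample correction and t on about 8 df; about 5–6% error. Cost: wider intervals. The t cut-off alone adds about 18% over the normal one (2.306 / 1.960).

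Options (a) and (b) assume a common treatment effect across sites, as the 5.1 model does; in the runs above only (c) stayed near 5% when the effect varied. The SAP should also say how the chosen degrees of freedom enter Rubin's rules, and which variance the logistic models will use. Only SAP wording changes; no additional data are needed.
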